8.1. Primary Efficacy Endpoint

The primary endpoint for Part 2 of the study is the time to fecal viral RNA clearance for subjects with a positive stool test for SARS-CoV-2 on Day 1 assessed by RT-qPCR in the niclosamide arm compared to the placebo arm.

Time to fecal viral RNA clearance is defined as the time (days) from the first dose of study treatment to the first stool RT-qPCR sample negative for SARS-CoV-2, after which all stool samples (if any) are negative. A stool sample is considered negative for SARS-CoV-2 if the test result is reported as “Not Detected”; otherwise, the stool sample is positive if the test result is reported as “Detected”. Furthermore, an “Inconclusive” test result is considered positive if it is followed directly by a positive test result; an “Inconclusive” test result is considered negative if it is followed directly by a negative test result. Subjects without fecal viral RNA clearance will be censored as follows:

- In the case of death of any cause, the subject will be considered to have the worst outcome with censoring at the planned Day 43 follow-up visit.
- In the case of hospitalization for any reason and withdrawal of consent, the subject will be considered to have the worse outcome with censoring at the planned Day 43 follow-up visit.
- In the case of study discontinuation prior to Day 43 follow-up visit due to any other reasons, the subject will be censored at the last available visit.
- In the case of study completion for Day 43, the subject will be censored at the date of the actual Day 43 follow-up visit.

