8.1.1. Primary Analysis

The analysis of the primary efficacy endpoint, time to fecal viral RNA clearance, will be conducted on the EE set.

The number and percentages of subjects achieving and not achieving the first fecal viral RNA clearance will be summarized up to each post-first dose study visit (Days 4, 8, 15, 22, 29, 36, and 43) by treatment group. For each study visit, only subjects with available assessment at the visit or having a negative stool test before the visit will be included in the summary and counted in the denominator for the percentages.

A stratified log-rank test will be used to compare time to fecal viral RNA clearance between niclosamide and placebo treatment groups adjusting for stratification factors, age (<65 years or ≥65 years) and sex (female or male). The two-sided p-value will be reported. The estimate of the hazard ratio (niclosamide vs. placebo) and the associated 95% confidence interval (CI) will be obtained from a Cox Proportional Hazards model adjusting for stratification factors and will also be reported.

Kaplan-Meier curves with 95% CIs will be generated for the total population by treatment group. Summary statistics obtained from Kaplan-Meier estimates, including the median time to fecal viral clearance with corresponding 95% CI and the proportion of subjects achieving fecal viral clearance at 3, 7, 14, 21, 28, 35, and 42 days post first dose (Day 1), will be summarized by treatment group.

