Date of the last watery stool between study visits will be collected on the Diarrhea Clinical Assessment eCRF. A summary table of events will include the number and percentage of subjects achieving and not achieving the last watery stool (followed by all formed stools) up to each post-first dose study visit (Days 4, 8, 15, 22, 29, 36, and 43) by treatment group. For each study visit, only subjects with available assessment at the visit or having the last watery stool before the visit will be included in the summary and counted in the denominator for the percentages.

Time to the last watery stool is defined as the time in days from the first dose of study treatment to the last watery stool (followed by all formed stools). Only subjects with baseline and at least one non-missing post-baseline will be included. Time to the last loose/watery stool during the course of the study will utilize the last visit at which a subject had watery stool. If a subject did not experience watery stool at any timepoint post-baseline, we impute time as 0.5 days. Subjects will not be censored because relapse cases of watery stool will be included in the analysis (i.e. subject experienced watery stool again after formed stool) and in such cases, the last visit at which relapse occurred is considered to be the last visit at which watery stool is experienced. Time to the last watery stool will be analyzed using the same time to event methods described for the analysis of the primary endpoint in [Section 8.1.1](#).

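### SAP 8.2.3 counts a subject whose last available assessment is still watery as having reached the last watery stool, against the section's own definition of the event

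*SAP*

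**What the plan says.** SAP 8.2.3 applies to subjects with Bristol type 6-7 stool on Day 1. It defines the endpoint as "the time in days from the first dose of study treatment to the last watery stool (followed by all formed stools" and closes the parenthesis there. Four further rules matter:

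- **Inclusion:** "Only subjects with baseline and at least one non-missing post-baseline will be included".
- **Time:** "Time to the last loose/watery stool during the course of the study will utilize the last visit at which a subject had watery stool", or 0.5 days if no post-baseline watery stool occurred.
- **Censoring:** none. "Subjects will not be censored because relapse cases of watery stool will be included in the analysis".
- **Summary table:** by visit, "the number and percentage of subjects achieving and not achieving the last watery stool (followed by all formed stools".

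The times then go into the SAP 8.1.1 methods: stratified log-rank test, Cox model and Kaplan-Meier estimates. For the primary endpoint the Kaplan-Meier output includes "the proportion of subjects achieving fecal viral clearance at 3, 7, 14, 21, 28, 35, and 42 days post first dose", so the corresponding proportions apply here.

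The other time-to-event endpoints, including SAP 8.2.2 (first formed stool) and 8.2.5 (abdominal symptoms), use the SAP 8.1 censoring rules for subjects who do not reach the event. For death: "In the case of death of any cause, the subject will be considered to have the worst outcome with censoring" at planned Day 43. For most other early exits: "due to any other reasons, the subject will be censored at the last available visit". SAP Section 14 records, in the past tense, that the last-watery-stool analysis needed no censoring.

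**The concern.** With one post-baseline assessment enough for inclusion, a time for everyone and no censoring, every included subject is an event. That is right for a subject with a watery stool followed only by formed stools. It is wrong for a subject whose last available assessment is watery, because nothing observed afterwards shows resolution. Three kinds of subject are affected: early exits while symptomatic, deaths while symptomatic, and completers still watery at Day 43.

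The stated reason does not reach them. Allowing for relapse settles which visit is the last watery one; it does not supply evidence of resolution after that visit. The by-visit table has a category for subjects who have not reached the event, so the same subject can be unresolved in the table and resolved in the Kaplan-Meier estimate.

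At stake are the reported proportion resolved and median duration in each arm and, if symptomatic exits differ by arm, the comparison between arms. An arm that loses more symptomatic subjects early would look faster.

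**Working it through.** The plan states no figure for this endpoint, so there is nothing to reproduce. The direction follows from the Kaplan-Meier formula. The sizes below are illustrations.

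**Direction.** The estimate is S(t) = product of (1 - d/n) over event times. Keep the times and risk sets fixed and relabel some events as censored: each d falls or stays the same, so each factor, and S(t), rises or stays the same. The SAP rule therefore never gives a lower proportion resolved, or a longer median, than censoring the same subjects at the same times.

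**Five-subject example.** Last watery visits are at 3, 3, 7, 14 and 42 days after first dose. The two at 3 days leave still watery, and the one at 42 days is still watery at Day 43.
- SAP rule: S(3) = 1 - 2/5 = 0.60; S(7) = 0.60 x (1 - 1/3) = 0.40. Median 7 days.
- Three unresolved subjects censored: S(7) = 1 - 1/3 = 0.67; S(14) = 0.67 x (1 - 1/2) = 0.33. Median 14 days.

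**Assumptions for the rest (not from the documents).** Resolution time T is exponential with median 14 days. A fraction p of subjects is set to leave at a day D uniform on 3 to 14, and does so only if still symptomatic then. Visits are at 3, 7, 14, 21, 28, 35 and 42 days after first dose, from the schedule.

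**Proportion with the event by 42 days, no exits.**
- SAP rule, visits on schedule: 100%, because a subject watery at Day 43 is an event at 42 days.
- SAP rule, actual dates, the seven days of the ±3-day window equally likely: subjects watery at a visit 43, 44 or 45 days after first dose fall beyond 42. 1 - (2^(-43/14) + 2^(-44/14) + 2^(-45/14))/7 = 1 - (0.119 + 0.113 + 0.108)/7 = about 95%.
- Censoring, visits on schedule: 1 - 2^(-42/14) = 87.5%.

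**Proportion with the event by 7 days.** With full follow-up, a last watery visit at 7 days or earlier means T < 14, so 50.0%.
- *Exiting subjects have no further assessment.* Everyone with T ≥ 14 who exits is backdated to the visit at 3 or 7 days, giving 0.5 + 0.5p.
- *Exiting subjects attend the early-termination assessment in Protocol 10.5.* Their time becomes D. The gain is limited to T ≥ 14 with D < 7: 0.5 x p x 4/11. Against it, subjects with D between 7 and 14 who would have recovered before day 14 move past day 7. The mean of 2^(-D/14) over that interval is 0.598, so this removes p x (7/11) x (0.598 - 0.5) = 0.062p. The range below is with and without that offset.

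| Assumed p | SAP rule, no further assessment | SAP rule, early-termination assessment attended | Censored, no further assessment (simulated) |
|---|---|---|---|
| 5% | 52.5% | about 51% | 49.6% |
| 15% | 57.5% | 52-53% | 48.8% |
| 30% | 65.0% | 54-55% | 47.3% |

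Deaths and losses to follow-up would not attend and others might, so the truth lies between the two SAP columns.

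**Arm comparison.** Simulation with no true difference, 14 per arm (an assumed size), medians 7 to 21 days, no early-termination assessment. One-sided significance favoring the high-exit arm under the SAP rule was 3.6-4.6% at 15% vs 5% exit and 5.4-9.6% at 30% vs 5%, against 2.6-2.7% with no exits. With equal 5% exit the SAP rule and censoring agreed within about 0.1 point.

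**Number of subjects.** The planned 30 stool-positive subjects per arm give 30 x 0.125 = 3.75 (Protocol 5.3, diarrhea among COVID-19 patients), 30 x 0.19 = 5.7 (Protocol 5.2, GI symptoms in one smaller study), or 30 x 0.77 = 23.1 (Protocol 5.2, overt GI symptoms among stool-positive patients, not all of it diarrhea). No Day 1 Bristol 6-7 count can be derived.

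**The case against.** The strongest case against has four parts.

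**The choice is open and the endpoint is minor.** The absence of censoring is stated in 8.2.3 and repeated in Section 14. The endpoint is secondary at nominal alpha, Part 1 has no inferential tests, and 8.2.2 is a censored companion. All of this stands and limits the weight of the point. But disclosing the rule does not reconcile it with the section's own definition.

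**The protocol endpoint has no resolution condition.** This stands. Protocol 8.2 speaks only of the last loose or watery stool, so a reader who infers a conflict with the protocol would be mistaken. The contradiction is within the SAP.

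**The Section 8.1 rules distort too.** This also stands. In the same simulation, censoring every early exit at Day 43 gave 7.6-9.6% significance against the high-exit arm (14 per arm, 30% vs 5%), about as large as the SAP rule's shift in its favor. The departure from 8.1 is therefore not itself the error, and the remedy need not be the worst-outcome rule.

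**Using the visit as the time matters more.** With a 14-day median, 1 - 2^(-7/14) = 29.3% have truly resolved by day 7, yet the last-watery-visit convention gives 50.0% even with full follow-up. That 20.7-point gap exceeds any censoring effect shown at 7 days. 8.2.3 also collects the date of the last watery stool, so the fix must say which is used.

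A reader might also infer that Section 14 shows nobody was last seen watery. It may mean that, or it may only restate the rule, under which nobody can be censored; the documents do not settle it.

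**Conclusion.** The point holds as an internal contradiction in SAP 8.2.3: subjects last seen watery are events, contrary to the section's definition and its by-visit table, and the relapse reason does not cover them. The direction of the effect on the proportion resolved and the median is certain relative to censoring the same subjects at the same times. Its size is not known, and every percentage above rests on assumed durations and exits.

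Three stronger readings are not supported:

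- That the 42-day proportion is 100% whatever the data. This needs visits on schedule; 8.2.3 does not say whether nominal or actual dates apply, and with actual dates the figure is about 95% under the stated assumptions.
- That the comparison is biased toward niclosamide or that its error rate is inflated. This needs symptomatic exits to differ by arm, for which the documents give no evidence. Stopping study drug is not study exit: Protocol 10.8.1 keeps such patients in follow-up.
- That the documents fix the number of affected subjects. They do not.

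The primary analysis is unaffected, and the effect is nil if no subject was last seen watery. Severity is minor to moderate.

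**What to change.** In SAP 8.2.3:

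1. Keep the relapse rule: the last watery stool is the latest one observed.
2. Count it as an event only if a later available assessment, including early termination, shows no watery stool. Deaths or withdrawals after documented resolution stay events.
3. Otherwise censor at the last available assessment, which for completers is the actual Day 43 visit.
4. State whether the event time is the collected date of the last watery stool or the visit.
5. Align Section 14, and report by arm the number of subjects last seen with watery stool.

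Censoring is not perfect: with no further assessment, the illustration puts it 0.4 to 2.7 points below the full-follow-up figure (50.0 - 49.6 and 50.0 - 47.3). The SAP rule overstates by 2.5 to 15.0 points in the same setting.

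The cost is SAP wording, one derivation change and one extra table row. No new data are needed. If nobody was last seen watery, items 1 to 3 leave the results unchanged.

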8.2.4. Proportion of subjects administered any anti-diarrheal agent during designated time periods

A summary table of anti-diarrheal agent administration will include the number and percentage (proportion) of subjects administered any anti-diarrheal agent during the following time periods by treatment group: first dose (Day 1) to Day 43 (inclusive), first dose (Day 1) to Day 8 (inclusive), first dose (Day 1) to Day 15 (inclusive), Day 16 to Day 29 (inclusive), and Day 30 to Day 43 (inclusive). A time period is defined if at least one visit unique to the time period exists. An anti-diarrheal agent will be considered administered during a specific time period if the calculation of days between the date of the first dose of study treatment and the start date of the anti-diarrheal agent falls within the specific time period. The use of anti-diarrheal agents along with start and end dates will be recorded on the Concomitant Medications eCRF at all study visits up to Day 43.

A Cochran Mantel-Haenszel (CMH) test will be used to compare the proportion of subjects administered any anti-diarrheal agent during each specified time period [first dose to Day 8 (inclusive), first dose to Day 15 (inclusive), and Day 16 to Day 29 (inclusive)] between niclosamide and placebo treatment groups adjusting for stratification factors, age (<65 years or ≥65 years) and sex (female or male). The two-sided p-value will be reported. The adjusted difference in proportions between the 2 treatment groups (niclosamide vs. placebo) will be computed as a weighted average of the treatment differences across strata using the Mantel-

Haenszel weights, and the associated 95% CI will also be provided using the Sato variance estimator ([Sato, 1989](#)).

8.2.5. Time from first dose of study treatment to improvement of abdominal symptoms

Only subjects with abdominal symptom(s) on Day 1 will be included in this analysis.

The overall severity of abdominal symptoms and the date of assessment will be collected on the Diarrhea Clinical Assessment. A summary table of severity will include the number of subjects with an assessment available and the number and percentage of subjects within each severity category at each study visit (Baseline, Days 4, 8, 15, 22, 29, 36, and 43) by treatment group. The proportion of subjects with any improvement from baseline of abdominal symptoms will also be provided in the summary table by treatment group. Improvement of abdominal symptoms is defined as any severity reduction from baseline by at least one level (i.e., mild to normal, moderate to mild or normal, or severe to moderate or mild or normal).

Time to the first improvement of abdominal symptoms is defined as the time in days from the first dose of study treatment to the first improvement of abdominal symptoms. Subjects without improvement of abdominal symptoms will be censored using the same rules as described for the primary efficacy endpoint in [Section 8.1](#). Time to improvement of abdominal symptoms will be analyzed using the same time to event methods as described for the analysis of the primary endpoint in [Section 8.1.1](#).

8.2.6. Proportion of subjects with a negative stool test for SARS-CoV-2 on Day 1 who acquire SARS-CoV-2 in stool through Day 43

This analysis will be conducted on the FAS and include only all subjects with a negative stool test for SARS-CoV-2 on Day 1.

A summary table will include the number and percentage (proportion) of subjects acquiring SARS-CoV-2 by treatment group first overall after Day 1 through Day 43 visit, then for each post-first dose study visit (Days 4, 8, 15, 22, 29, 36, and 43). For each study visit, only subjects with available assessment at the visit or having a positive stool test before the visit will be included in the summary and counted in the denominator for the percentages.

8.3. Systemic and Respiratory Secondary Efficacy Endpoints

The analysis of the systemic and respiratory secondary efficacy endpoints will be conducted on the FAS.

8.3.1. Proportion of subjects with each WHO severity score by study visit

The WHO severity score and the date of assessment will be collected on the WHO Ordinal Scale for Clinical Improvement eCRF. A summary table severity will include the number of subjects with an assessment available and the number and percentage (proportion) of subjects with each WHO severity score at each study visit (Baseline, Days 4, 8, 15, 22, 29, 36, and 43) by treatment

group. The proportion of subjects with any clinical improvement or clinical worsening of illness severity from baseline will also be provided in the summary table by treatment group. Clinical improvement of illness severity is defined as a 1-point or greater reduction from baseline in WHO severity score. Clinical worsening of illness severity is defined as a 1-point or greater increase from baseline in WHO severity score.

Time to first clinical improvement of illness severity is defined as the time in days from the first dose of study treatment to the first clinical improvement of illness severity. Subjects without clinical improvement of illness severity will be censored using the same rules as described for the primary efficacy endpoint in [Section 8.1](#). As a supportive analysis, time to clinical improvement of illness severity will be analyzed using the same time to event methods as described for the primary endpoint in [Section 8.1.1](#).

8.3.2. Total duration, method of administration, and quantity of supplemental oxygen treatment

A summary table by treatment group will include the following:

- Number and percentage of subjects who require supplemental oxygen
- Number and percentage of subjects with each method of oxygen administration
- Descriptive statistics for the total number of days requiring supplemental oxygen

A subject will be considered as requiring supplemental oxygen if the subject is administered any supplemental oxygen from first dose through Day 43. The total number of days requiring supplemental oxygen will be calculated by taking the sum of the duration (stop date – start date +1) for each supplemental oxygen treatment. The start and stop date of supplemental oxygen treatment, oxygen type, method of oxygen supplementation, oxygen flow rate and FiO₂ will be collected on the Supplemental Oxygen Treatment eCRF at all study visits up to Day 43.

8.3.3. Proportion of subjects with normal body temperature by study visit

A summary table will include the number of subjects with an assessment available and the number and percentage of subjects with normal body temperature at each study visit (Baseline, Days 4, 8, 15, 22, 29, 36, and 43) by treatment group. Normal body temperature is defined for each method of measurement as follows: $\leq 36.9^{\circ}\text{C}$ axillary, $\leq 37.4^{\circ}\text{C}$ oral, $\leq 37.8^{\circ}\text{C}$ rectal, and $\leq 37.5^{\circ}\text{C}$ tympanic ([Geneva et al., 2019](#)).

8.3.4. Proportion of subjects with normal blood oxygen saturation by pulse oximetry (SpO₂) on room air by study visit

A summary table will include the number of subjects with an assessment available and the number and percentage (proportion) of subjects with normal SpO₂ on room air, defined as SpO₂ >90%, at each study visit (Baseline, Days 4, 8, 15, 22, 29, 36, and 43) by treatment group. The oxygen saturation (%) on room air will be collected on the Vital Sign eCRF.

8.3.5. Proportion of subjects admitted to the intensive care unit (ICU) and length of ICU stay

A summary table containing the proportion of subjects admitted to the ICU from the first dose through Day 43 and the length of ICU stay for each treatment group will be presented. The length of ICU stay in days will be calculated by taking the sum of the duration (discharge date – admission date + 1) for each ICU admission. ICU admissions and dates of stay will be captured on the Hospitalizations eCRF.

8.3.6. Time to nasopharyngeal viral clearance assessed by RT-PCR

Only subjects with positive test on Day 1 will be included in this analysis.

Time to nasopharyngeal viral clearance is defined as the time in days from the first dose of study treatment to the first nasopharyngeal RT-PCR sample negative for SARS-CoV-2. Subjects without nasopharyngeal clearance will be censored using the same rules as described for the primary efficacy endpoint in [Section 8.1](#).

A summary table will include the number and percentage of subjects achieving and not achieving the first nasopharyngeal viral clearance up to each post-first dose study visit (Days 4, 8, 15, 22, 29, 36, and 43) by treatment group. For each study visit, only subjects with available assessment at the visit or having a negative nasopharyngeal test before the visit will be included in the summary and counted in the denominator for the percentages.

Time to nasopharyngeal viral clearance will be analyzed using the same time to event methods as described for the analysis of the primary endpoint in [Section 8.1.1](#).

8.3.7. Proportion of subjects requiring hospitalization and duration of hospitalization from first dose through Day 43

Hospital admissions and dates of stay will be captured on the Hospitalizations eCRF.

Summary table containing the proportion of subjects requiring any hospitalization and the duration of hospitalization will be presented for each treatment group. A subject will be considered as requiring hospitalization if the subject has at least one hospital admission with an admission date between the first dose date and the Day 43 follow-up visit date (inclusive). The duration of hospitalization in days will be calculated by taking the sum of the duration (discharge date – admission date + 1) for each hospitalization.

9. Safety Analysis

Safety analyses will be conducted on safety data collected through the Day 43 follow-up visit for all randomized subjects and will be included as part of the Day 43 Final Analysis for the main CSR. All safety analyses will be performed using the SAF set and will be presented separately for Part 1 and Part 2 of the study unless otherwise specified.

